### 10.1 Primary Efficacy Analysis

The Recruitment Primary Outcome will be calculated as described in Section 6.4.

The Retention Primary Outcome treatment group percentages will be compared using Boschloo's Test at the 2-sided 5% significance level under the null hypothesis that retention rates are equal between treatment groups [15]. The maximum likelihood estimate of the odds ratio of treatment retention to control retention will be computed with a 2-sided 95% confidence interval and p-value.

The Rating of Recommending Intervention to Friend and Rating of Recommending Intervention to Those with Chronic Pain items will be summarized using an ordinal regression (proportional odds) model without predictors (i.e., the ordinal properties of the Likert scales of these two items will be respected by estimating the average rating adjusted for the cumulative category response probability distribution) [16]. The modified Intention-to-Treat sample described in Section 8.1 will be used.

The Length of Intervention Time will be calculated as described in Section 6.4.

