to WCM/NYP physicians for permission to contact potential patient participants. Research staff will set EPIC search criteria to draw names from all networked EPIC databases accessible to Weill Cornell Medicine staff. Identified potential participants will be contacted via recruitment letter, email, or Weill/EPIC Connect. Recruitment letters may also be sent to potential participants via EPIC pool of WCM/NYP Consent to be Contacted for Research (CCR) patients and chart review to determine potential eligibility. Potential subjects will be sent a letter informing them of the study and that they will be contacted by a co-investigator who will assess interest in participating in the study. The letter will also provide a contact phone or email address that these patients can reach out to express their interest/disinterest for participation in the study.

Additional efforts will rely on making study information available on online platforms. Online platforms may include, but are not limited to: FMS interest pages on Facebook, participant registries, online bulletin boards, mobile apps and websites, etc. Methods include, but are not limited to: posting flyers, posting messages describing the project and inviting interested participants to contact study members (see "Social Media Posting" document), including study information in e-newsletters, etc. Permission from group administrators will be received prior to posting on any social media group platform. In addition, online research match databases including but not limited to ResearchMatch.org and the Institute for Translational Health Sciences will be added as a recruitment method.

Eligible participants will be compensated up to \$142 for completing the study. Participants will receive \$25 for each of the three study assessments (baseline, post-intervention, and 1-month follow up), up to \$42 (\$2 per survey) for the daily 5-10-minute surveys following the study assessments, and \$25 for the feedback survey. Activities completed during the 6-8 weeks of interaction on BrightOutcome will not be compensated.

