## **5.2 Endpoints**

### **5.2.1 Primary Endpoints**

**5.2.1.1** Recruitment as Measured by Rates of Enrollment

**5.2.1.2** Retention as Measured by Change in Enrollment

**5.2.1.3** Helpfulness, Satisfaction, and Impact as Assessed by Self-Report Participant Feedback Survey

**5.2.1.4** Length of Intervention Time as Measured by Number of Weeks to Complete Intervention

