#### **6.4.1.3 Helpfulness, Satisfaction, and Impact as Assessed by Self-Report Participant Feedback Survey**

##### **6.4.1.3.1 Rating of Recommending Intervention to Friend**

The item is measured on an 11-point Likert scale for which 0=Definitely Not to 10=Definitely Yes. Assessed at Post-Intervention.

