**8      General Analysis Considerations****8.1    Analysis Populations****8.1.1    Modified Intention to Treat Population**

All subjects who received any study drug and who participated in at least one post-baseline assessment (i.e., all randomized participants with data following the treatment intervention window).

Participants may be removed from the Modified Intention to Treat Population for analysis if they have (a) no observed data on Post-Intervention assessments, (b) withdrew consent during the study, or (c) were unable to access the online intervention and daily emotion reporting platform.

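### The two primary acceptability ratings describe only LARKSPUR participants who gave Post-Intervention data and stayed in the modified ITT sample, so acceptability is likely, though not certainly, overstated

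*SAP*

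**What the plan says.** SAP 5.2.1 lists as a primary endpoint "Helpfulness, Satisfaction, and Impact as Assessed by Self-Report Participant Feedback Survey". SAP 6.4.1.3 defines it through two items: recommending the intervention to a friend, and to people with chronic pain. Both carry the same definition: "The item is measured on an 11-point Likert scale for which 0=Definitely Not to 10=Definitely Yes. Assessed at Post-Intervention". SAP Table 1 marks the Feedback Survey at Post-Intervention only. SAP 6.1 says that the primary outcomes other than retention characterise the treatment group and are not tested.

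SAP 10.1 says the two items "will be summarized using an ordinal regression (proportional odds) model without predictors", and adds "The modified Intention-to-Treat sample described in Section 8.1 will be used".

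SAP 8.1.1 defines that sample as "All subjects who received any study drug and who participated in at least one post-baseline assessment", explained as randomised participants with data after the intervention window. It then permits removal for (a) "no observed data on Post-Intervention assessments", (b) withdrawal of consent, or (c) inability to access the intervention and daily-reporting platform. The removals are permissive, and no rule says when they apply.

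For missing data, SAP 8.3 relies on mixed models with participant random intercepts, checked by comparing the modified ITT results with complete cases. Protocol 8 promises suitable imputation; the SAP names none for these items.

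**The concern.** Acceptability is half of the first study aim, and the pilot is meant to inform a larger trial. People who found the programme unhelpful or burdensome are the most informative about poor acceptability, and they are plausibly less likely to give Post-Intervention data. An average over those who did is conditional on staying.

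Removal (c) adds a second selection. LARKSPUR is delivered only online, so someone who could not reach the platform is a person for whom delivery failed. The Protocol runs the intervention on BrightOutcome and the assessments in REDCap or by phone, so such a person could still answer the survey and then be dropped from the summary.

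If the summary is read as the acceptability of LARKSPUR to those offered it, a high average could partly reflect who was left to answer.

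**Working it through.** **No plan figure to reproduce.** The documents state no expected rating, acceptability target or cut-off.

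**Can the planned methods recover a missing rating?**
- The proportional odds model has no predictors. It reproduces the observed category proportions, so its average is the observed average of those rated. It borrows no information about anyone else.
- A random-intercept model uses a participant's other measurements of the same outcome. Each item is measured once, so a person without a rating contributes nothing.
- A person without a rating is in neither the modified ITT summary nor the complete-case summary of that item. Comparing the two says almost nothing about non-raters.
- SAP 8.3 seeks reasons for discontinuation where possible, but no rating is collected then.

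**Inputs for the illustration**
- r, share of the LARKSPUR arm rated: 0.80. This is past retention in the emotion-reporting control condition (Protocol 3, Attention Control Condition), described there as similar to or above that of the intervention. It is a proxy for LARKSPUR, not a stated LARKSPUR figure.
- Arm size: 75 (Protocol 3), so 60 rated and 15 not. With the SAP 7 target of 45 it is 36 and 9. The means below are the same for both.
- Mean among raters: 8 (assumed). Mean that non-raters would have given: 0, 4, 8 or 10 (assumed; 0 and 10 are the scale limits).

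**Formulas**
- Mean over all randomised = r × (rater mean) + (1 − r) × (non-rater mean)
- Overstatement = (1 − r) × (rater mean − non-rater mean)

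**Results at 80% rated, rater mean 8**

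| Non-raters would give | Mean over all 75 | Reported 8 minus this |
|---|---|---|
| 0 | (60×8 + 15×0)/75 = 6.4 | +1.6 |
| 4 | (60×8 + 15×4)/75 = 7.2 | +0.8 |
| 8 | (60×8 + 15×8)/75 = 8.0 | 0 |
| 10 | (60×8 + 15×10)/75 = 8.4 | −0.4 |

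**Sensitivity to the assumptions**
- Rater mean 7, 80% rated: bounds 5.6 to 7.6; 6.4 if non-raters give 4.
- Rater mean 9, 80% rated: bounds 7.2 to 9.2; 8.0 if non-raters give 4.
- Rater mean 8, 68 of 75 rated (about 90%): bounds 544/75 = 7.25 to 614/75 = 8.19; 572/75 = 7.63 if non-raters give 4.

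The width of the bounds is 10 × (1 − r), or 2 points at 80%, whatever the raters say.

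**The case against.** The strongest reply is that the loss is already visible. Post-Intervention retention is a separate primary outcome over all enrolled at Baseline (SAP 6.4.1.2). Attrition reasons and a CONSORT diagram are planned (SAP 9.1), and summary tables show non-missing counts and the table's total population (SAP 9). All analyses are exploratory and no decision rule depends on the mean. This lowers the stakes, and a careful reader could work out rough bounds. It does not connect the loss to the ratings: the total for a modified ITT table may be read as the modified ITT size, and retention counts do not show ratings discarded under the removal rules.

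Four stronger readings are tempting but not supported:

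- *Everyone who leaves LARKSPUR early goes uncounted.* Someone who stops the lessons but completes Post-Intervention meets the entry condition. The removals are optional, and the Protocol provides reminders and phone or video assessment to support retention.
- *Acceptability is shown to be overstated.* No ratings exist for non-raters, and the bounds lie on both sides of the reported value.
- *A returned survey would be excluded under (a).* The Feedback Survey is itself a Post-Intervention item, so returning it arguably defeats (a). The separate payment for it does not show separate handling. Removals (b) and (c) can still apply.
- *The SAP expects one-third loss, because it recruits 45 to secure 30.* SAP 7 ties that allowance to losses after the end of the trial period and before follow-up, which come after this survey.

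**Conclusion.** The point holds as a limitation of analysis set and reporting on a primary endpoint. The ratings describe LARKSPUR participants who gave Post-Intervention data and were not removed. Upward bias is the likelier direction, on the assumption that dissatisfied people are less likely to respond; neither its sign nor its size can be established from the documents.

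Under the assumed rater mean of 8 with 80% rated, the overstatement is 0.8 points if non-raters would give 4, at most 1.6, and could be as low as −0.4. The plan has no sensitivity analysis that would show this range. The selection through removal (c) is avoidable, because it can discard ratings already in hand. The change is worth making before analysis, but the issue does not undermine the trial.

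**What to change.** In SAP 10.1, for these two items only:

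1. Replace the modified ITT sentence with: *all participants randomised to LARKSPUR who return the Feedback Survey, whatever their modified ITT status, subject to consent for use of data*.
2. Report the number rated out of all randomised to LARKSPUR beside each average.
3. Add best- and worst-case bounds on the mean, setting non-respondents to 10 and 0, as the sensitivity analysis for these items in place of the SAP 8.3 comparison.

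In the description of the schedule, state that the existing Post-Intervention Feedback Survey also goes, at its scheduled date, to LARKSPUR participants who stopped the lessons early. This makes explicit what the schedule already allows. Widening the analysis set cannot create ratings that were never collected, so this step is needed as well.

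Cost: a few lines of SAP text, a little more analysis, and no new instrument; the $25 survey payment is already planned (Protocol 4.4). If the clarification is also written into the Protocol, it follows the usual amendment route. The downside is a headline average shown with wider and possibly less favourable bounds, and some early leavers will still not reply.

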## 10.2 Secondary Efficacy Analyses

Exploratory interaction analyses along demographic (ethnicity, race) and clinical covariates will assess treatment effect heterogeneity for the primary outcome analyses in Section 10.1 by summarizing/testing Primary Outcomes by subgroup.

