with basic skills for recognizing and savoring positive events and progressing to more complex skills such as goal-setting and acts of kindness.

A week will consist of 1-2 days of didactic material and 5-6 days of real-life skills practice and reporting. Participants cannot skip ahead and can only progress to the next lesson if they have completed the current one, but they can return to old lessons or exercises if they choose. As part of the daily home practice, intervention participants will be asked to complete the daily emotion check-in that comprises the attention control condition (which takes about 5 minutes to complete). Based on past studies, we estimate the time to read through a skill to be about 15 minutes per skill. We also encourage daily interaction with the website (home practice, reporting emotions) and estimate the time involved to be an additional about 10 minutes. Both the LARKSPUR intervention and emotion-reporting attention control conditions, including all home practice and assessments, will be done over the internet from the participant's home, or any other location of their choice. The intervention content, emotion check-in, and are all mobile-enabled so can be completed on desktop, laptop, tablet, or smartphone with web browser access.

Attention Control Condition (n = 75). We sought an attention control condition that provided something to engage participants, but was not expensive or burdensome. In past research we have established that emotion reporting is acceptable as an attention control condition (retention rates of ~80%, similar to or higher than for the intervention), and that participants perceive it as being beneficial, providing some of the features of a placebo control. In this daily emotion-reporting attention control condition, participants will be asked to report how they are feeling daily for 6-8 weeks which will be emailed to control participants.

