## **6 Study Methods**

### **6.1 General Study Design and Plan**

The trial is a randomized, longitudinal, parallel-group, attention-controlled trial. Treatment allocation is a 1:1 ratio. Participants are randomly assigned to LARKSPUR or an emotion-reporting-only attention control condition stratified by race/ethnicity; non-Hispanic Black, Hispanic, or non-Hispanic other (e.g., White, Asian) after completion of eligibility screening

and baseline assessments (see Table 1 for the schedule of trial events). All participants will know their intervention/attention control status.

The LARKSPUR study protocol states that one of the Primary Outcomes is to establish feasibility (Retention as Measured by Change in Enrollment), so Retention will be tested for superiority.

The LARKSPUR study protocol states that the secondary objectives include hypotheses that “intervention participants will report more frequent PA, decreased depressive symptoms, enhanced physical functioning, improved stress appraisals, and reduced FMS pain (intensity and interference) immediately following the intervention (approximately 8 weeks), and at 1-Month Follow-Up.” Therefore, all Secondary Endpoints will be tested for superiority.

Other Primary Outcomes characterize the treatment group only and are not tested statistically.

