**8.2    Covariates and Subgroups**

Baseline covariates for each secondary outcome are expected to correlate with their matching secondary outcome scores at Post-Intervention and 1-Month Follow-Up assessments. Therefore, analyses of each secondary outcome will include participant Baseline scores for adjustment of superiority analyses of treatment differences.

Race/ethnicity was used to stratify treatment allocation and will be adjusted for in primary analyses if sample sizes within each race/ethnicity—treatment subgroup is sufficient (i.e., greater than 5). Otherwise, race/ethnicity will be omitted from primary analyses.

Given the pilot nature of the study, sample size was chosen based on feasibility indicators (recruitment, retention, adherence) rather than on formal power calculations [see 1]. Accordingly, interaction analyses comparing treatment effects by race/ethnicity, age and gender are exploratory.

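### SAP 10.2 calls its subgroup work interaction analyses, but the only method it states is summarising or testing Primary Outcomes by subgroup, and no treatment-by-subgroup term is written anywhere in SAP 10 to 10.2.1

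*SAP*

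**What the plan says.** SAP 10.2 opens with "Exploratory interaction analyses along demographic (ethnicity, race) and clinical covariates" and says that these "will assess treatment effect heterogeneity for the primary outcome analyses in Section 10.1 by summarizing/testing Primary Outcomes by subgroup". Nothing further is specified.

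SAP 8.2 says that "interaction analyses comparing treatment effects by race/ethnicity, age and gender are exploratory", but names no outcome and no model. Its separate provision to adjust for race/ethnicity when cells are large enough is a main effect, not an interaction.

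On which Primary Outcomes compare the arms:
- SAP 6.1 says retention is tested, and then: "Other Primary Outcomes characterize the treatment group only and are not tested statistically".
- SAP 10.1 agrees. Retention is "compared using Boschloo's Test at the 2-sided 5% significance level under the null hypothesis that retention rates are equal between treatment groups", and an odds ratio with a 95% confidence interval is reported.
- In SAP 10.1 the two recommendation ratings get an "ordinal regression (proportional odds) model without predictors", while recruitment and length of intervention time are simply calculated.

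The objective of exploring racial/ethnic disparities is in SAP 5.1.1.2, alongside pain, positive affect, depressive symptoms, physical functioning and stress appraisals. The interactions written into the models for those outcomes (SAP 10 and 10.2.1) involve treatment, time and day in burst only.

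**The concern.** A treatment effect is heterogeneous when the arm difference itself differs between subgroups. Separate tests in each subgroup do not measure that. With small strata, one can cross the 5% line and another miss it although the underlying effect is the same in both. An analyst who follows the stated method could therefore report a racial/ethnic difference in retention effect that the data do not support.

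Two further gaps follow from the text. Recruitment, the feedback ratings and length of intervention time have no arm contrast, so they have no treatment effect that could vary; recruitment is also settled before randomisation. And the outcomes to which the disparities objective is attached have no heterogeneity model at all.

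The factor lists also disagree. SAP 10.2 names ethnicity, race and unspecified clinical covariates; SAP 8.2 names race/ethnicity, age and gender. Allocation uses one combined three-level variable. The choice of factors is thus open until the data are seen.

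**Working it through.** The documents give no power, error rate or sample size for the subgroup analysis, so there is no plan figure to reproduce. The check asks how often by-stratum testing of retention gives a mixed result when there is no heterogeneity.

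**Inputs**
- Test: Boschloo, two-sided 5% (SAP 10.1).
- Strata: three, with equal enrolment targeted (Protocol 4.4). Exactly equal strata are an assumption.
- Size: 45 per group (SAP 7) gives 45/3 = 15 per arm per stratum. The Protocol's 75 per group (section 3, Randomization) gives 75/3 = 25. Both were run.
- Retention: the documents' only information is the attention-control paragraph of Protocol section 3, "retention rates of ~80%, similar to or higher than for the intervention". Control is set at 80%. The LARKSPUR rates of 80%, 75%, 70% and 60% are assumptions.

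**Method.** For each scenario, let q be the probability that one stratum is significant. It is found by enumerating every possible pair of retained counts, weighting by binomial probabilities, and summing where the Boschloo p-value is at most 0.05. With three independent strata sharing the same true rates,

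P(some but not all significant) = 1 − (1 − q)³ − q³.

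| LARKSPUR v control, same in every stratum | q, 15 per arm | mixed result | q, 25 per arm | mixed result |
|---|---|---|---|---|
| 80% v 80% | 0.043 | 12% | 0.038 | 11% |
| 75% v 80% | 0.053 | 15% | 0.057 | 16% |
| 70% v 80% | 0.082 | 22% | 0.112 | 30% |
| 60% v 80% | 0.192 | 46% | 0.324 | 66% |

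For example, at 60% v 80% with 15 per arm: 1 − 0.808³ − 0.192³ = 1 − 0.528 − 0.007 = 0.465.

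When there is no effect, the mixed-result rate stays below the nominal 1 − 0.95³ = 14.3%. Across common retention rates of 60% to 90%, the chance that at least one stratum is significant is about 6% to 13%.

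**Comparison with a homogeneity test.** A Woolf test of equal odds ratios (0.5 added to each cell, 2 df, 200,000 simulated trials) was run on the same strata.
- Common 60% v 80%: it signals heterogeneity in about 2% (15 per arm) or 3% (25) of trials, against 46% or 66% mixed results from separate tests.
- True heterogeneity, with 50% v 80% in one stratum and 80% v 80% in the other two: its power is about 13% or 27%.

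**Precision of the interaction estimate.** At 80% retention throughout, the variance of one stratum's log odds ratio with 15 per arm is 2 × [1/(15×0.8) + 1/(15×0.2)] = 0.833. The standard error of the log ratio of two such odds ratios is √(2 × 0.833) = 1.29, so the 95% limits lie a factor of exp(1.96 × 1.29), about 12.6, either side of the estimate. With 25 per arm the variance is 0.5, the standard error is 1.0 and the factor is about 7.1.

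**The case against.** The sentence in SAP 10.2 does begin by calling the work exploratory interaction analysis, and SAP 8.2 speaks of comparing treatment effects. The text never says that the tests are run separately or that inference rests on them. That is fair. The defect is a label that the stated method does not deliver, and within-subgroup testing is the natural reading rather than an explicit commitment.

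A reader might infer that chance patterns will be reported as disparities. The documents do not support that. The analyses are labelled exploratory in SAP 8.2, 10 and 10.2; SAP 7 asks for caution on subgroup findings and for confirmatory trials; and SAP 8.4 calls for confidence intervals beside p-values. The one retention figure given points to small gaps between arms, where the mixed-result rate is nearer 11% to 30% than 46% to 66%.

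A reader might also infer that 10.2 contradicts 6.1 by testing outcomes that 6.1 says are not tested. The documents do not force this: the combined term for summarising and testing can mean summarising the untested outcomes and testing retention. What stands is that subgroup summaries of those outcomes cannot show treatment effect heterogeneity.

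Nor does 10.2 lead directly to a claim that LARKSPUR is effective in one racial/ethnic group and not another. Its only arm contrast is retention, which says nothing about benefit on pain or mood.

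Listing ethnicity and race separately matches the reporting categories in SAP 9.2.1, so that part is minor for description. Low power of an interaction test is a sound reason not to expect an answer from this pilot. It is no reason to prefer stratum p-values.

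**Conclusion.** The concern holds in a limited form. SAP 10.2 states a method that does not assess the heterogeneity it names. The interaction it promises is not specified in SAP 10 to 10.2.1, and only retention among the Primary Outcomes has an effect to which it could apply. For retention, the chance of a mixed result without heterogeneity is modest if the arms retain equally and large only if a sizeable common gap exists. These figures assume three equal, independent strata and 80% control retention. The 10- and 20-point gaps are illustrations, not figures from the documents. The conclusion is the same at 45 or 75 per group. The SAP's cautions lower the risk of misreading, but they do not tell the analyst which model to fit.

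**What to change.** 1. **Retention.** In SAP 10.2, replace by-subgroup testing with the treatment-by-race/ethnicity interaction, using the three-level randomisation stratifier. Report ratios of odds ratios with 95% confidence intervals, which extends the odds ratio already in SAP 10.1. Show retention percentages by arm and stratum without p-values. State how a cell with no dropouts is handled: at 80% retention and 15 per cell its probability is 0.8¹⁵ = 3.5%, or 1 − 0.965⁶ = 19% for at least one of the six cells.
2. **Recruitment, feedback ratings and length of intervention time.** Describe by stratum, and do not call this treatment effect heterogeneity.
3. **Secondary outcomes.** Add an exploratory treatment-by-race/ethnicity term to the mixed models of SAP 10 and 10.2.1, reported as estimates with confidence intervals. This is where the disparities objective of SAP 5.1.1.2 lies.
4. **Factors.** Use one list in 8.2 and 10.2, with each clinical covariate named.

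The cost is SAP wording and a few extra model runs, with no change to conduct or data collection. The downside is that the interaction intervals will be wide and visibly inconclusive, which is an honest account of what a pilot of this size can show.
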